#### 6.2 Timing of Evaluations

## 6.2.1 Screening

# Screening

Screening evaluations to determine eligibility must be completed within 42 days prior to entry unless otherwise specified and must occur prior to the participant starting any study medications, treatments, or interventions.

In addition to data being collected on participants who enroll into the study, demographic, clinical, and laboratory data on screening failures will be captured in a Screening Failure Results form and entered into the ACTG database.

## 6.2.2 Entry Evaluations

Entry evaluations must occur at least 24 hours after all screening evaluations have been completed. Entry evaluations must be performed before study treatment is started.

Participant must be fasting (i.e., no food or drink, except water for taking prescription medications, for at least 8 hours) for the lipid panel and TFV PK evaluation at entry.

Participant must begin study treatment within 48 hours after randomization.

#### 6.2.3 Post-Entry Evaluations

# Step 1: On-Treatment Evaluations

On-treatment (Step 1) visits are scheduled in reference to the date of study entry. Weeks 1 and 2 have a window of  $\pm 3$  days. Weeks 4, 8, 12, 16, 20, and 24 have a window of  $\pm 7$  days. Only those participants randomized to Arm B will have weeks 16, 20, and 24 on-treatment evaluations.

#### Step 2: Post-Treatment Evaluations

Participants will be registered to Step 2 at their last on-treatment visit. R is the date of the last dose of study treatment. Arm A participants will register to Step 2 at week 12. Arm B participants will register to Step 2 at week 24. Participants who prematurely discontinue study treatment will register to Step 2 at the premature treatment discontinuation visit.

After the last dose of study drugs, the post-treatment study visits have the following windows:

- Week R+4: -5 days to +7 days
- Week R+12: -5 days and +14 days
- Week R+24: -7 days and +14 days

# Study Completion Evaluations

The week R+24 visit will be completed as the participant's final study visit.

#### 6.2.4 Event Driven Evaluations

## HCV Virologic Failure/Relapse Confirmation

Participants with suspected HCV VF, as defined in section 7.3, must have a confirmation sample obtained as soon as possible, but within 2 weeks of initial notification of HCV RNA meeting criteria for HCV VF. Participants who permanently discontinue study treatment for HCV VF (see details in section 7.3) will be followed on study/off treatment in Step 2 per the SOE.

Virologic evidence of HCV relapse, defined as HCV RNA <LLOQ at end-oftreatment but HCV RNA ≥LLOQ during follow-up, will require confirmation and the sample should be obtained and the sample sent in real time to the designated laboratory as soon as possible but within 2 weeks after determination of initial observation. The results will be provided to the site investigators within 2 weeks of specimen receipt.

#### HIV-1 Virologic Failure (VF) Confirmation

Participants with suspected HIV-1 virologic failure, as defined in section 7.1.6, must have a confirmation sample obtained within 2 weeks after the initial sample was drawn. In addition, participants must complete the evaluations listed for HIV-1 VF Confirmation, as per section 6.1. If the HIV-1 VF confirmation visit coincides with a regularly scheduled visit, the evaluations should be combined.

Participants with confirmed HIV-1 RNA ≥200 copies/mL will have a corresponding stored sample submitted for HIV-1 resistance genotyping.

Participants confirmed to have HIV-1 VF will continue to be followed on study/off study treatment per the Schedule of Events (SOE), if an HIV-1 regimen compatible with study treatment is available. If there are no HIV-1 regimens available that are compatible with study treatment, then the participant must discontinue study treatment and will be followed on study/off study treatment per the SOE (see details in section 7.1.6).

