## 5.4.1 Required Medications

See inclusion criteria (section 4.1.5) for specifications about ARV. Changes to ARV must be discussed with the A5348 protocol core team during the study drug dosing period.

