#### HCV RNA (on-study evaluations)

At the entry and post-entry visits, HCV RNA quantification will be performed at the designated testing laboratory) as follows:

Serum HCV RNA real-time testing will be collected, processed, and shipped to the designated testing laboratory (see A5348 laboratory processing chart [LPC] for instructions). These results will be reported within 2-3 weeks after specimen receipt.

NOTE: The study team should be notified ([contact]) of detectable HCV RNA after week 4 of study treatment.

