### 7.1.6 HIV-1 Virologic Failure

Plasma HIV-1 RNA will be monitored throughout the study for participants on ARV. In this study, HIV-1 viral failure will be defined as confirmed increase in HIV-1 RNA to  $\geq$ 200 copies/mL at any time after study entry, only for participants who are taking ARV.

Since "blips" in HIV-1 RNA may be observed in individuals on ARV in the absence of HIV-1 VF, any increase in plasma HIV-1 RNA ≥200 copies/mL must be confirmed with repeat testing as soon as possible (not to exceed 2 weeks). For participants with confirmed HIV-1 VF, a plasma specimen obtained at the time of confirmation will be sent to the designated central laboratory for evidence of HIV-1 drug resistance. Confirmed HIV-1 VF specimens must have repeated detection of ≥200 copies/mL for HIV-1 drug resistance testing. Results will be reported back to sites in real-time from the designated central laboratory.

Clinical management of HIV-1 VF will be handled by local site investigators according to current HIV treatment guidelines and local standard of care. The A5348 protocol core team must be contacted to notify of any changes in ARV regimen in the event of HIV-1 VF ([contact]).

Investigators should consult section 5.0 and the package insert.

Regarding the potential for a modified ARV regimen for HIV-1 VF: Possible modified ARV regimens should take into account the unique characteristics of the participant and the participant's HIV treatment history as well as known and/or anticipated drug interactions with DAA or DAA+RBV therapy.

If no reasonable salvage HIV regimens compatible with continued HCV DAA or DAA+RBV therapy are deemed available for an individual participant with HIV-1 VF then the participant must discontinue HCV DAA+RBV therapy.

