### 8.0 CRITERIA FOR DISCONTINUATION

- 8.1 Premature Study Treatment Discontinuation
  - Drug-related toxicity (see section 7.1 Toxicity).
  - Pregnancy in a female participant or in the female partner of male participant.
  - HCV failure as defined in section 7.3.
  - Failure by the participant to attend three or more consecutive clinic visits.
  - Seven or more missed consecutive doses of study treatment.
  - Participant requests to discontinue for any reason.
  - Requirement for prohibited concomitant medications (see section 5.4).
  - Breastfeeding.

• Clinical reasons believed life threatening by the physician, even if not addressed in the toxicity section of the protocol.

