This document describes the proposed content for the interim review reports and the primary statistical analysis report for ACTG study A5348, focusing on analyses that address the safety and HCV virologic outcome measures. The plan includes the key analyses that will form the core of any presentation or publication used to disseminate the primary conclusions of the study. It also includes analyses in interim reports for the Study Monitoring Committee (SMC) while the study is ongoing and describes the components shared with the Study Chairs in open interim reports. It is recognized that this statistical analysis plan (SAP) may be modified by the Study Team as new information becomes available or to reflect recommendations made by the SMC.

SAP Version 2.0: The study closed to accrual prematurely on July 21, 2016 due to the enrollment challenges. The SAP version 2.0 removes analysis components that are no longer feasible or applicable based on 7 study participants, and it updates planned analyses. The final analysis report will be descriptive, with the goal of contributing to the sponsor company's (Gilead's) manuscript on a similar clinical trial.

2 Study Overview

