4.2.5 Virologic Failures

- a) HIV Virologic Failure

- Details on participants on ART with undetectable HIV RNA at entry who experience HIV-1 virologic failure (as defined in the protocol), including adherence to study regimen and ARV medications, and dose modifications to study medications and ARVs.
- b) HCV Virologic Failures
 - Details on participants who experience HCV virologic failure (as defined in the protocol), including ARV regimen, adherence to study regimen and ARV medications, dose modifications to study medications and ARVs, and the following baseline information: HCV RNA, cirrhosis status, race and ethnicity, HCV genotype, development of resistance-associated variant at the time of virologic failure.
- ✓ SDAC validation: All programs generating variables as study-specific will be validated (e.g. HIV breakthrough, HCV breakthrough).

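### Protocol 6.2.4 gives the off-treatment status to participants with HIV-1 virologic failure who still have a compatible HIV regimen, against 7.1.6; one word needs changing

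*Protocol*

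**What the plan says.** Protocol 6.2.4 (HIV-1 Virologic Failure Confirmation) has two branches for a participant whose HIV-1 failure is confirmed.

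- **A compatible regimen exists.** Such participants "will continue to be followed on study/off study treatment per the Schedule of Events (SOE), if an HIV-1 regimen compatible with study treatment is available".
- **No compatible regimen exists.** In that case, "then the participant must discontinue study treatment and will be followed on study/off study treatment per the SOE", with a reference to 7.1.6 for details.

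Protocol 7.1.6 defines HIV-1 failure as a confirmed rise to at least 200 copies/mL in participants taking ARV. Its stopping rule has one condition: "If no reasonable salvage HIV regimens compatible with continued HCV DAA or DAA+RBV therapy are deemed available for an individual participant with HIV-1 VF", HCV therapy must be discontinued. It also asks investigators choosing a new ARV regimen to consider interactions with the HCV drugs.

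Protocol 5.4.1 foresees ARV changes while HCV treatment is under way: "Changes to ARV must be discussed with the A5348 protocol core team during the study drug dosing period".

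Protocol 8.1 lists reasons for stopping study treatment early. It includes "HCV failure as defined in section 7.3" and does not name HIV-1 failure.

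**The concern.** The two branches of 6.2.4 rest on opposite conditions and give the same status. Whether a compatible HIV regimen exists therefore changes nothing in the follow-up label, although that is the question the paragraph asks. The first branch also conflicts with 7.1.6, where a compatible regimen is what allows HCV therapy to go on.

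This is an operative patient-management instruction, in the section a site would consult after a confirmed HIV-1 failure. Read literally, it takes a participant off HCV treatment in a population the protocol describes as hard to treat. Such a stop is not easily reversed. Under 6.2.5, premature discontinuation leads to Step 2 registration, and 4.3.1 makes permanent discontinuation a condition of entering Step 2.

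**Working it through.** **Comparing the text**

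| Situation | 6.2.4 | 7.1.6 |
|---|---|---|
| Compatible HIV regimen available | Off treatment; no order to discontinue | No order to stop; new regimen chosen with HCV drug interactions in mind |
| None available | Must discontinue; off treatment | Must discontinue |

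The only order to discontinue in the 6.2.4 paragraph is in the second row. The preceding HCV failure paragraph of 6.2.4 uses the off-treatment status for participants who have permanently stopped study drug.

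Two other readings were considered.

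- *The first branch is meant for participants already in Step 2.* Compatibility with study treatment would then be irrelevant.
- *Every participant with HIV-1 failure is meant to stop.* The condition would then be pointless, and 7.1.6 would be contradicted.

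Replacing *off* with *on* in the first branch makes the rows differ and agree with 7.1.6. The Letter of Amendment items shown do not touch the sentence.

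**Treatment that could be lost by one affected participant**

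Inputs:

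- Planned duration: 12 weeks (Arm A), 24 weeks (Arm B).
- Scheduled post-entry HIV-1 RNA visits (6.1): weeks 4, 12, 24 (Arm B) and R+4. Those before the end of dosing are week 4 in either arm and week 12 in Arm B. Triggers at Arm A week 12, Arm B week 24 or R+4 cost no treatment.
- Confirmation sample: within 2 weeks of the first draw (6.2.4).
- HIV-1 RNA turnaround: not given. For on-study HCV RNA, 6.3.8 says "These results will be reported within 2-3 weeks after specimen receipt". For confirmatory HCV RNA, 7.3 allows 2 weeks from receipt.

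Let d be the weeks from trigger sample to confirmed result. This is an assumption, run from a fast case of 1 week to a slow case of 2 + 3 = 5 weeks. With the confirmatory HCV turnaround, d = 2 + 2 = 4.

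Weeks lost = planned duration − trigger week − d.

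| Trigger | Formula | d = 1 | d = 4 | d = 5 |
|---|---|---|---|---|
| Arm A, week 4 | 12 − 4 − d | 7 (58%) | 4 (33%) | 3 (25%) |
| Arm B, week 4 | 24 − 4 − d | 19 (79%) | 16 (67%) | 15 (63%) |
| Arm B, week 12 | 24 − 12 − d | 11 (46%) | 8 (33%) | 7 (29%) |

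The ceilings at d = 0 are 8, 20 and 12 weeks, which cannot be reached in practice. Visit weeks are nominal; the ±7-day window moves each figure by up to one week.

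**When the correction could still protect anyone**

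The SAP introduction states: "The study closed to accrual prematurely on July 21, 2016 due to the enrollment challenges". Adding 24 weeks (168 days) to 21 July 2016 gives 5 January 2017. Adding the 48 hours that 6.2.2 allows for starting treatment gives 7 January 2017. SAP Version 2.0 cites a call on 6 January 2017 (section 2.9), so dosing was over or ending by then.

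**The case against.** The strongest reply is that this is an editorial slip with almost no practical reach. Much of that stands.

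- **The paragraph half-corrects itself.** The condition makes no sense for someone off treatment, the order to stop is in the other branch, and 7.1.6 is cited. Core-team contact about ARV changes (5.4.1, 7.1.6) would often prevent a wrongful stop.
- **Few participants could be affected.** Entry on ARV requires a stable regimen for more than 8 weeks and HIV-1 RNA below 50 copies/mL within 42 days (4.1.5c). Only seven participants enrolled, and nothing in the documents shows that any had HIV-1 failure.
- **The 5-week delay is generous.** If the first result took 3 weeks, a confirmation sample could not be drawn within 2 weeks of the first. Four weeks fits the protocol's rule better. This raises the lower bounds of weeks lost to 4, 16 and 8, so the ranges above err towards understatement.
- **The scheduled visits are not the only possible triggers.** Section 7.1.6 sets no visit restriction after entry, so an unscheduled sample could also count.
- **Section 8.1 is weak evidence.** It omits HIV-1 failure even for the case where stopping is mandatory. The conclusion does not depend on it.
- **Section 7.1.6 never says outright that the others stay on treatment.** That is inferred from its conditional stop and its reference to continued therapy. The inference is strong.

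None of this makes the first branch correct as written or changes the remedy.

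**Conclusion.** The concern holds. The first branch of 6.2.4 carries the wrong treatment status, very likely a slip of one word, and it conflicts with the section it cites. The potential cost is confined to individual participants on ARV whose HIV-1 failure is confirmed during dosing while a compatible regimen exists. For them it is 3–7 of 12 weeks in Arm A, or 15–19 (week-4 trigger) or 7–11 (week-12 trigger) of 24 weeks in Arm B. These figures rest on the assumed delay of 1 to 5 weeks and on the site following the label literally. The documents give no HIV-1 failure rate; the frequency is likely low. No effect on sample size, estimand or arm-level SVR12 is claimed. The correction was worth making while participants were being dosed; afterwards its value is an accurate record.

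**What to change.** In the first branch of the HIV-1 failure paragraph of 6.2.4, change *off* to *on*, so that participants with a compatible HIV regimen are followed on study and on study treatment. HCV treatment then stops only when no compatible regimen is available, as in 7.1.6.

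The cost is one word, in a clarification memo or a Letter of Amendment. Data collection, analysis and the SAP stay as they are. To see whether anyone was stopped wrongly, use two existing outputs together. The SAP 4.2.5 listing of HIV-1 failures reports details "including adherence to study regimen and ARV medications, and dose modifications to study medications and ARVs", but only for participants on ART with undetectable HIV RNA at entry. The SAP 4.1.5 summary of reasons for treatment discontinuation, with its listing of reasons coded as other, covers the rest.

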6.2.5 Discontinuation Evaluations

Evaluations for Randomized Participants Who Do Not Start Study Treatment Participants who do not start study treatment will be taken off study with no further evaluations required. All CRFs must be completed and keyed for the period up to and including entry.

## Premature Treatment Discontinuation Evaluations

The protocol core team must be informed, as soon as possible, when a participant prematurely discontinues study treatment due to an AE. Participants who permanently discontinue study treatment for toxicity or any other reason, and who have not met the HCV virologic failure criteria defined in section 7.3 will also follow the Step 2 schedule in section 6.1. If applicable, additional or more frequent post-treatment toxicity follow up may be determined by the site

investigator.

Participants who prematurely discontinue study treatment (i.e., prior to completion of the last dose of LDV/SOF per the assigned dosing period) will complete the premature treatment discontinuation evaluations within 7 days of discontinuation and be registered to Step 2 (R). Participants will remain on study and complete the post-treatment visits at weeks R+4, R+12, and R+24 weeks per the SOE.

Participants who prematurely discontinue the study treatment for any reason will register for Step 2 at their Premature Treatment Discontinuation Visit.

NOTE: If LDV/SOF is discontinued, Arm A participants should discontinue RBV. Under no condition should the participant remain on RBV monotherapy.

## Pregnancy

Pregnancy will result in immediate and permanent discontinuation of the study medications. Please see section 7.2 for detailed information regarding participant management. Participants will be followed on-study/off-treatment per the SOE.

# Premature Study Discontinuation Evaluations

Participants who prematurely discontinue from the study will have the study discontinuation evaluations performed prior to being taken off the study.

6.3 Instructions for Evaluations

All clinical and laboratory information required by this protocol is to be present in the source documents. Sites must refer to the Source Document Guidelines on the DAIDS Web site for information about what must be included in the source document: http://www.niaid.nih.gov/labsandresources/resources/daidsclinrsrch/documents/sourced ocappndx.pdf

All stated evaluations are to be recorded on the CRF and keyed into the database unless otherwise specified. This includes events that meet the International Conference on Harmonisation (ICH) definitions for a serious adverse event:

- Results in death
- Life-threatening
- Requires inpatient hospitalization or prolongation of existing hospitalization
- Results in persistent or significant disability/incapacity
- Congenital anomaly/birth defect
- Other important medical event (may not be immediately life-threatening or result in death or hospitalization but may jeopardize the patient or may require intervention to prevent one of the events listed above.

To grade diagnoses, signs and symptoms, and laboratory results, sites must refer to the DAIDS Table for Grading the Severity of Adult and Pediatric Adverse Events, Version 2.0 (November 2014), which can be found on the DAIDS RSC Web site:

http://rsc.tech-res.com/safetyandpharmacovigilance/gradingtables.aspx

6.3.1 Documentation of HIV-1

Section 4.1.4 specifies assay requirements for HIV-1 documentation. HIV-1 documentation will not be recorded on the CRF.

6.3.2 Documentation of Cirrhosis Status

Section 4.1.2 specifies requirements for documentation of cirrhosis status. Documentation will be recorded on the CRF.

6.3.3 Documentation of Prior HCV Treatment and Response

Section 4.1.8 and the table below specify requirements for documentation of prior HCV treatment and its response. This documentation will be recorded on the CRF.

Past Treatment Response Category	Definition	Past Treatment Response Sub-category
Treatment-Intolerant	Participant discontinued prior HCV treatment due to a laboratory abnormality or intolerable side effect. Participant did not meet a virologic failure criterion.	N/A
Non-Responder	Participant did not achieve undetectable HCV RNA levels (HCV RNA ≥ LLOQ) while on HCV treatment. This was the reason for discontinuing treatment rather than an AE.	For PEG-IFN/RBV non- responders, participants should be further defined as Null or Partial Responders: Null Responders: HCV RNA <2 Log10 reduction during the first 12 weeks of treatment. Partial Responders: HCV RNA ≥2 Log10 reduction during the first 12 weeks of treatment.
Relapse/Breakthrough	Participant achieved undetectable HCV RNA levels (HCV RNA < LLOQ) during HCV treatment,	Relapse: Participant achieved undetectable HCV RNA levels (HCV RNA < LLOQ) at end of treatment but HCV RNA

Table 6-1: Prior HCV Treatment and Response

Past Treatment Response Category	Definition	Past Treatment Response Sub-category
	but did not achieve a SVR. If treatment was discontinued early, it was because of breakthrough rather than an AE.	became detectable after treatment was stopped, at or before 24 weeks after treatment discontinuation. Breakthrough : Participant experienced ≥1 log increase in HCV RNA from nadir while on treatment.

# 6.3.4 Medical History

In addition to reporting all diagnoses within the past 42 days, the following diagnoses should be reported regardless of when the diagnosis was made:

- AIDS-defining conditions
- Bone fractures (verbal history accepted)
- Coronary heart disease
- Cancer (exclusive of basal/squamous cell skin cancer)
- Diabetes
- Tuberculosis
- Chronic hepatitis B

Any allergies to any medications and their formulations must also be documented.

# 6.3.5 Medication History

A medication history must be present, including start and stop dates. Table 6-2 below lists the medications that must be included in the history.

# Table 6-2: Medication History

Medication Category	Complete History or Timeframe
HIV treatment	Within 56 days prior to entry
HCV treatment	Complete history
Prescription drugs	Within 42 days prior to entry
Non-prescription drugs	Within 42 days prior to entry
Complementary and alternative	Within 42 days prior to entry
therapies	

# 6.3.6 Clinical Assessments

# Complete Physical Exam

A complete physical examination must be performed at screening and is to include at a minimum an examination of the head, neck and thyroid; eyes, ears, nose, throat, mouth and tongue; chest (excluding breasts); respiratory; cardiovascular; lymph nodes, abdomen; skin, hair, nails; musculoskeletal; neurological.

The complete physical exam will also include diagnoses, signs, and symptoms and vital signs (temperature, pulse, respiratory rate, and resting blood pressure).

NOTE: Blood pressure will be measured following the current ACTG Standardization of Blood Pressure Measurement SOP.

